10.2 Methods and Timing for Assessing, Recording, and Analyzing Safety Parameters

Our interventions are informational and logistical and designed to enhance safe, patient-centered approaches to patient care. If they were to prompt, for instance, less opioid use, in theory, that could lead to worse function or increase pain. That is why we chose the composite outcome measure of pain and physical function. Whether it is accurate to associate that “risk” to our intervention itself, versus the treatments prompted by our intervention is a topic of debate. Nevertheless, this is a minimal risk study. If we conservatively assume that downstream prescribing practices are attributable to our interventions, usual care (using opioid medications as a first line approach to pain management in the acute and post-acute recovery periods following a surgical procedures) introduces greater risk of dependency, addiction, and overdose, than those posed by the intervention we are providing in the NOHARM trial which is guideline concordant.

10.3 Adverse Events and Serious Adverse Events

Adverse Event (AE): Any untoward or unfavorable medical occurrence resulting unambiguously from the misuse or overuse of non-pharmacological pain management strategies facilitated by the intervention. All untoward or unfavorable medical occurrences will be first assumed to be associated with the patient’s surgery. Untoward or unfavorable medical occurrences will be deemed an adverse event only if they can be clearly associated with use of non-pharmacological pain management strategies recommended and/or facilitated by the intervention and could not, under any circumstances, have otherwise happened.

Serious Adverse Event (SAE): Any adverse event unambiguously associated with the intervention that:

- Results in death

- Is life threatening, or places the participant at immediate risk of death from the event as it occurred
- Requires or prolongs hospitalization
- Causes persistent or significant disability or incapacity
- Results in congenital anomalies or birth defects
- Is another condition which investigators judge to represent significant hazards

There are no laboratory or other clinical values which may be used to assess safety concerns related to the intervention. Patient reported pain, requests for assistance with pain management, and other health outcomes, while measurable, are associated with the patient's surgical procedure and will be gathered as part of the ultimate outcome data. If patients were to experience a paradoxical response to a modality –massage, for example – those effects would likely be transient and they would have access to all the usual care resources of Mayo Clinic as any other patient should those symptoms persist.

Adverse events that may be anticipated in the study involve any patient misuse or overuse of non-pharmacological pain management strategies. Patients who elect to incorporate non-pharmacological pain management strategies in their recovery from surgery will be instructed in the use of those strategies, including whether (and when) the use of those strategies is appropriate in their situation.

Because non-pharmacological pain management modalities recommended by the intervention are guideline concordant approaches to pain management under normal circumstances, they will be monitored by the patient's surgical team as a part of usual post-acute care. Therefore, we will not actively review for potential events with scheduled promptings.

Unprompted adverse events are possible, but not expected. Surgical teams will inform the study team if they are made aware of any untoward medical occurrence that could reasonably be attributed to a patient's misuse or overuse of non-pharmacological pain strategies as a direct result of the facilitation provided by the NOHARM intervention. Such events are highly unlikely, and the risks of such events leading to unfavorable outcomes is almost non-existent. The risks of participant cooperation in the NOHARM intervention is far less than the risks of usual care which often involve opioid medications alone in the acute and post-acute recovery periods.

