10.3.1 Reporting Procedures

An AE or SAE will be suspected if a member of the patient's surgical team or any member of the study team who interfaces with the patient for any reason suspects that a patient is experiencing a medical issue that is unambiguously related to the patient's interaction with the NOHARM intervention.

The principal investigator, relevant study team members, and any relevant members of the surgical team will adjudicate the relevance of the patient's experience to the NOHARM intervention (versus an anticipated result of the patient's surgical procedure).

If a patient experience or outcome is determined to be an AE or SAE by protocol definition, then that patient's experience will be documented and reported per institutional procedures. The surgical team and/or members of the study team with expertise in post-surgical pain management will follow up with that patient to ensure that appropriate steps are taken to mitigate any negative outcomes and ensure that the patient is properly informed and educated about safe use of non-pharmacological pain management strategies for the remainder of their surgical recovery.

Severity of the Event

All AEs will be assessed by a qualified medical professional using a protocol defined grading system.

Mild – Events require minimal or no treatment and do not interfere with the participant's daily activities.

Moderate – Events result in a low level of inconvenience or concern with the therapeutic measures. Moderate events may cause some interference with functioning.

Severe – Events interrupt a participant's usual daily activity and may require systemic drug therapy or other treatment. Severe events are usually potentially life-threatening or incapacitating. Of note, the term "severe" does not necessarily equate to "serious".

Relationship to the Study Intervention

Because this is a minimal risk study and the intervention may be construed as less risky than usual care, it would be inappropriate to regard the study intervention as suspect, by default, for all medical occurrences in the perioperative period. For this reason, the principal investigator, clinical experts on the study team, and the patient's surgical team will adjudicate the relevance of patient events outcomes in a binary fashion:

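### The AE/SAE definition sets a causal test that postoperative events can hardly meet, and the notification, suspicion and recording rules around it do not agree

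*Combined protocol and SAP*

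**What the plan says.** Section 10.3 defines an adverse event as an occurrence "resulting unambiguously from the misuse or overuse of non-pharmacological pain management strategies" that the intervention facilitates. It then sets a default cause: "All untoward or unfavorable medical occurrences will be first assumed to be associated with" the patient's surgery. Two conditions follow, joined by an "and". Occurrences "will be deemed an adverse event only if they can be clearly associated with use of non-pharmacological pain management strategies" recommended or facilitated by the intervention, and they must be such that they "could not, under any circumstances, have otherwise happened". A serious adverse event is an adverse event, unambiguously associated with the intervention, that also meets one of the usual seriousness criteria.

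The same section says there will be no scheduled review for events. Surgical teams are to inform the study team of "any untoward medical occurrence that could reasonably be attributed to" a patient's misuse or overuse of the strategies, where this results directly from the facilitation the intervention provides.

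Section 10.3.1 says an AE or SAE is suspected when a member of the surgical or study team "suspects that a patient is experiencing a medical issue that is unambiguously related" to the patient's interaction with the intervention. The investigator, study team and surgical team then decide, as a yes/no question, whether the event is related. Unrelated is the presumption. Events found to meet the protocol definition are documented and reported.

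Section 10.3.2 says that every suspected event will be documented and the record updated if the event is later judged an AE or SAE. It also says that the study coordinator records the events that are reportable under the definitions.

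**The concern.** A safety count is informative only if it can rise when harm rises. The definition here asks for proof that an event had no other possible cause, in patients who have all just had an operation. If that test decides what is called an AE or SAE, the reported count will be low whether the strategies are harmless or not.

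The second problem is that staff meet several thresholds in a few pages. Someone following the notification sentence in section 10.3 and someone following section 10.3.1 could treat the same event differently, and the protocol does not say which governs.

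This matters more because few other safety provisions are visible. Section 10.1 pre-specifies no safety parameters, section 10.3 excludes active review, and section 12.3 plans no interim analysis and no stopping rules. The intervention also includes physical modalities: Appendix B says the trial will buy TENS units for the clusters.

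**Working it through.** The plan gives no AE rate and no figure to reproduce, so the check is a comparison of the wordings.

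**1. The thresholds side by side**

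| Step | Section | Causal standard | Scope |
|---|---|---|---|
| Notification by surgical teams | 10.3, closing part | reasonable attribution | misuse or overuse |
| Suspicion | 10.3.1 | "a medical issue that is unambiguously related to" the patient's interaction with the intervention | any interaction |
| AE, first sentence | 10.3 | unambiguous result | misuse or overuse |
| AE, third sentence | 10.3 | clear association, and no other possible origin | use |
| SAE | 10.3 | must be an AE, plus unambiguous association and seriousness | as for AE |
| Documentation | 10.3.2 | suspected | as for suspicion |
| Coordinator's record | 10.3.2 | meets the definitions | as for AE |

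From loosest to strictest, the causal standards are reasonable attribution, unambiguous relation, and no other possible origin. The strictest decides AE status.

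**2. Is the strict clause binding?** Yes. The sentence is an "only if" with two conditions joined by "and", so an event that is clearly associated with a strategy still fails if it could have happened otherwise. Because an SAE must first be an AE, a death or a prolonged hospital stay faces the same test.

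**3. A case from the protocol itself.** Section 10.3 foresees a paradoxical response to massage. Suppose the massage was given as instructed and the patient's pain rose.
- First sentence of the definition: not an AE, because there was no misuse or overuse.
- Third sentence, association: met, since use is enough.
- Third sentence, no other origin: failed, since pain can rise after surgery without massage.
- Notification sentence: not covered, because it is limited to misuse or overuse.
- Section 10.3.1: possibly suspected, since any interaction with the intervention counts.
- Section 10.3.2: documented if suspected, but absent from the coordinator's record because it does not meet the definition.

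One event therefore gets different answers depending on which sentence is applied.

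**4. What this does to the count.** Let n be the patients exposed, r the true rate of related events, p1 the probability that such an event is notified or suspected, and p2 the probability that it is then classified as an AE. The expected AE count is n × r × p1 × p2. The no-other-origin clause pushes p2 toward zero, so the count is small for any r. The mismatch between sections 10.3 and 10.3.1 makes p1 depend on which text a team follows, and the absence of active review lowers p1 further. The documents give none of r, p1 or p2, so only the direction can be stated.

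**5. No comparator.** The definition ties an AE to strategies facilitated by the intervention, so control periods generate no AE count against which a low figure could be judged.

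**The case against.** The best defence is that the text describes a sequence: teams notify broadly, suspected events are documented, a group adjudicates, and a strict definition decides what is finally called an AE. A loose first step before a strict last one is no contradiction, and the adjudication step is already in section 10.3.1. This stands in part. It does not explain why section 10.3.1 sets a stricter trigger for suspicion than the notification sentence, why the definition says both misuse or overuse and use, or why section 10.3.2 has two recording rules. It also does not make the final test attainable.

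Four stronger readings are tempting, and the documents do not support them.

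- *Almost nothing will be recorded.* Section 10.3.2 requires all suspected events to be documented. The definition limits what is classified and reported as an AE or SAE, not every record.
- *Harm from reduced opioid use can never be seen.* Section 10.2 concedes that less opioid use "in theory, that could lead to worse function or increase pain" and gives this as the reason for choosing pain and function as the outcome. Sections 12.4.1 and 12.5 then measure and compare both by intervention status. For a harm common after any surgery, that comparison is more informative than case-by-case attribution.
- *The monitoring board would be misled.* Section 13.3.4 says safety data will be made available to the board, and Appendix B lists a board charter and a monitoring plan that are not part of these documents. What the board sees cannot be judged from them.
- *The shortfall can be stated as a multiple.* Any such figure would come from an assumed event rate and an assumed capture rate, and would show only those assumptions.

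**Conclusion.** The point holds as a defect in classification and reporting. The test for AE status is stricter than the notification and suspicion wordings, few postoperative events can pass it, and the SAE definition carries it over. A low AE/SAE count from this trial would therefore say little about safety. Separately, the wordings in sections 10.3, 10.3.1 and 10.3.2 are inconsistent on scope, trigger and record, and need reconciling.

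The size cannot be quantified, because no event rate or capture probability is given. The conclusion rests on reading the "only if ... and" sentence as written, and on the premise that most events after surgery have a conceivable surgical cause, which section 10.3 itself presumes. An injury specific to one device might still qualify, so near-unattainable is the right description and impossible is not. The definition is also not the only cause of a low count: passive ascertainment and the presumption of unrelatedness would contribute even with better wording.

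**What to change.** Amend sections 10.3, 10.3.1 and 10.3.2 together:

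1. Set one threshold for notification, suspicion and recording, for example an event that could reasonably be attributed to use of a strategy the intervention facilitates. The existing notification sentence cannot be taken over unchanged, because it carries the misuse-or-overuse restriction.
2. Delete the clause requiring that the event could not have happened otherwise, and remove the restriction to misuse or overuse from the first sentence of the AE definition.
3. Leave relatedness to the adjudication already in section 10.3.1, applied after recording.
4. Have the coordinator's record include every suspected event with its adjudicated relatedness, so that readers can see how many were raised and how many were ruled out.
5. When safety is reported, show hospitalizations and ER visits by intervention status beside the AE count. Both are already collected and modelled under sections 12.4.2 and 12.5. Use the model estimates adjusted for calendar time as well as crude rates, since intervention status and calendar time are linked in a stepped wedge.

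The cost is a short amendment, a matching change to what teams are told, and a modest number of extra events to document and adjudicate. No new data collection from patients is needed. If the change is made after some tranches are active, its date should be recorded, because counts before and after it are not comparable.

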10.3.1 Reporting Procedures

An AE or SAE will be suspected if a member of the patient's surgical team or any member of the study team who interfaces with the patient for any reason suspects that a patient is experiencing a medical issue that is unambiguously related to the patient's interaction with the NOHARM intervention.

The principal investigator, relevant study team members, and any relevant members of the surgical team will adjudicate the relevance of the patient's experience to the NOHARM intervention (versus an anticipated result of the patient's surgical procedure).

If a patient experience or outcome is determined to be an AE or SAE by protocol definition, then that patient's experience will be documented and reported per institutional procedures. The surgical team and/or members of the study team with expertise in post-surgical pain management will follow up with that patient to ensure that appropriate steps are taken to mitigate any negative outcomes and ensure that the patient is properly informed and educated about safe use of non-pharmacological pain management strategies for the remainder of their surgical recovery.

Severity of the Event

All AEs will be assessed by a qualified medical professional using a protocol defined grading system.

Mild – Events require minimal or no treatment and do not interfere with the participant's daily activities.

Moderate – Events result in a low level of inconvenience or concern with the therapeutic measures. Moderate events may cause some interference with functioning.

Severe – Events interrupt a participant's usual daily activity and may require systemic drug therapy or other treatment. Severe events are usually potentially life-threatening or incapacitating. Of note, the term "severe" does not necessarily equate to "serious".

Relationship to the Study Intervention

Because this is a minimal risk study and the intervention may be construed as less risky than usual care, it would be inappropriate to regard the study intervention as suspect, by default, for all medical occurrences in the perioperative period. For this reason, the principal investigator, clinical experts on the study team, and the patient's surgical team will adjudicate the relevance of patient events outcomes in a binary fashion:

- Not related to the NOHARM intervention. This will be the presumption, unless proven otherwise. Patients may be expected to have many challenges to overcome following a surgical procedure. These challenges are unrelated to the intervention.
- Related to the NOHARM intervention. The study team will evaluate all occurrences suspected of being associated unambiguously with the NOHARM intervention and adjudicate their relevance. We do not expect any AEs or SAEs to result from the NOHARM intervention.

10.3.2 Follow-up for Adverse Events

Patient events suspected of being AEs or SAEs will be addressed immediately by the Principal Investigator, relevant experts on the study team, and/or the patient's surgical team. Upon determination that an event is indeed an AE or SAE, appropriate actions will be taken, including contacting the patient and providing instructions.

All events suspected of being AE will be documented, and documentation for recorded events subsequently determined to be an AE or SAE will be updated. All AEs and SAEs will be followed to adequate resolution.

The study coordinator will record all events reportable by the definitions above occurring any time following patient enrollment and limited to the last data collection point in the study. All events are expected to occur in the acute or early post-acute periods of recovery.

10.4 Safety Monitoring

The Data and Safety Monitoring Board and/or Safety Officer appointed by the NIA will monitor the conduct of the study.

11 **INTERVENTION DISCONTINUATION**

This study is a pragmatic clinical trial, and as such, patients will not be individually consented. However, voluntariness is preserved as patients and surgical teams are not required to engage with any component of the intervention they are not interested in or deem irrelevant to their care. Additionally, as a pragmatic clinical trial, “the intervention” will be systematically implemented at the surgical practice level, per the stepped-wedge schedule, as an element of usual care.

Therefore, discontinuation of the study, whether for an individual participant or for all participants at once is defined as the cessation of study measurement prespecified by the study timeline. The discontinuation of the study intervention components, if merited, will be at the discretion of the surgical specialties in conjunction with the DSMB; discontinuation is not anticipated.

Removal individual patients from the trial will be functionally achieved in the following situations:

- The patient actively requests to have their records withdrawn from the NOHARM study dataset. This is unlikely, as patients will only know of NOHARM as a practice-based care initiative per the pragmatic design of the trial.
- Patients previously indicating their unwillingness to have medical record data used for research purposes will have their records redacted from final study datasets prior to analysis.

Cessation of study measurement will happen for the entire trial in the event that:

- Institutional needs / priorities preclude our ability to conduct study procedures (e.g. in the case of institutional response to COVID-19).
- The study funder requests that study activities cease.

In the event that an individual patient withdraws from the study or the entire study ceases, patients will still be monitored by their surgical team per usual care practices for the duration of their post-acute recovery period. Cessation of study procedures will not impact patients’ access to standard supportive care following surgery.

12 STATISTICAL CONSIDERATIONS

12.1 General Design Issues

This study will address the primary objective using a cluster randomized stepped wedge design. Surgical practices, or clusters, will be randomized in 5 tranches to receive the NOHARM intervention; outcomes of patients treated by these teams will be compared by intervention status of the team. The primary statistical hypothesis is that pain and function measures will be lower and higher, respectively, in the patients treated under the intervention conditions, when compared with non-intervention patients in those same practices.

The cluster randomized stepped-wedge design will allow us to stagger the NOHARM implementation while increasing statistical power. The alternative to staggering the implementation would be to implement at all sites at the same time, which is impractical from a resource perspective. The stepped-wedge design allows each site to serve as its own control, reducing the bias due to imbalanced risk factors across clusters. Contamination does pose some threat to the internal validity of stepped wedge designs when, as here, the intervention rolls out sequentially in adjacent clusters. The 22 NOHARM clusters will minimize potential contamination by capitalizing on geographical separations in the built environments used to deliver perioperative care including different buildings in some cases, as well as subspecialty-designated inpatient wards, office suites, etc.

The primary hypothesis is that the NOHARM intervention will reduce patient reported pain and increase patient reported function following designated surgical procedures relative to patients treated under usual care. The primary outcome – a composite of patient reported pain and function – 3 months post-operatively will be assessed using validated patient reported outcomes.

